 Yes X No	Include the use of radiation? (x-ray imaging, radiopharmaceuticals, external beam or brachytherapy)	
Complete the AURPC Human Use Application and follow instructions on the form for submission to the AURPC committee.
 
Contact: [contact]
	Approval from these committees must be received prior to IRB approval;
 Yes X No	Use the Center for Magnetic Resonance Research (CMRR) or MR at Masonic Institute for the Developing Brain (MIDB) as a study location?	
Complete the CMRR pre-IRB ancillary review
 
Contact: [contact]
	These groups each have their own application process.
 Yes X No	Include the use of recombinant or synthetic nucleic acids, toxins, or infectious agents?	
STOP – Complete the Medical Template Protocol (HRP-590)
	
 Yes X No	Include the use of human fetal tissue, human embryos, or embryonic stem cells?	
STOP – Complete the Medical Template Protocol (HRP-590)
	
X Yes  No	Include PHI or are you requesting a HIPAA waiver?	
If yes, HIPCO will conduct a review of this protocol.
 
Contact: [contact]
	
 Yes X No	Plan to use CTSI Monitoring services, and/or have an IND, IDE, or designated NSR-IDE by the UMN IRB?	
The CTSI monitoring ancillary review will be assigned to your study by IRB staff.
 
Please note eligibility criteria here.
 
Contact: [contact]
	Approval must be received prior to IRB approval.
 Yes X No	
Use data from CTSI Best Practices Integrated Informatics Core (BPIC)
 
Formerly the AHC Information Exchange (AHC-IE)?
	
The Information Exchange ancillary review will be assigned to your study by IRB staff
 
Contact: [contact]
	
 Yes X No	Use the Biorepository and Laboratory Services to collect tissue for research?	
STOP – Complete the Medical Template Protocol (HRP-590)
 
The BLS ancillary review will be assigned to your study by IRB staff.
	These groups do not have a separate application process but additional information from the

SOCIAL PROTOCOL (HRP-580)

PROTOCOL TITLE: Time toxicity of cancer: the time demands of cancer-related activities and their impact on well-being and quality of life

VERSION DATE: 02/27/2024

1.0 Objectives

1.0 Purpose: Our overall objectives are to 1) measure, describe, and quantify sources of cancer-related time toxicity among individuals treated for cancer, and their effect on QOL; and 2) create time toxicity scores which can be used in future studies to identify opportunities to minimize time toxicity. Our specific aims are:

Aim 1: Measure and describe components of objective time use associated with cancer-related healthcare interactions via a mobile health application.

Aim 2: Characterize associations between measures of cancer-related time use and self-reported well-being, and explore the role of context in modifying these associations.

Aim 3: Create a time toxicity summary score based on measures of cancer-related time use and assess its association with psychosocial outcomes.

2.0 Background

2.1 Significance of Research Question/Purpose: Cancer-related demands on patients' time and stress have multiple sources: time spent on care itself (appointments, taking medication), travel and wait times, and other activities such as scheduling, paperwork, dealing with bills and insurance, and organizing one's schedule in order to accommodate time for these activities. *The time spent on these activities competes with time patients would otherwise dedicate to loved ones, work, childcare, preventive care, caregiving, household activities, or leisure time.* Leisure time serves as a buffer to cope with negative life events through distraction, adaptation, self-restoration, and stress compensation, enabling better coping with cancer.[1, 2] The burdens of care can only be fully understood in the context of and in interaction with other time and labor demands. *Accurately defining and measuring time toxicity as both the direct and indirect time burdens of cancer and related treatments is a necessary first step for identifying effective interventions to address them.*

Whether cancer-related tasks and time use become a toxic burden depends on unique patient situations. Disadvantaged patient populations and those with multiple other responsibilities are likely to be most affected, and some of these populations bear a disproportionate cancer burden.[3, 4] For example, low-income patients and some ethno-racial minority groups experience more pain and symptom burden, more financial distress, lower survival rates, and poorer QOL.[5-7] Other vulnerable groups include: women who, despite shifts in traditional family roles, often still carry significant household and family responsibilities in addition to contributing to family incomes; populations with limited geographic access to cancer care [8] such as rural populations with long travel distances to clinics; and those with

SOCIAL PROTOCOL (HRP-580)

PROTOCOL TITLE: Time toxicity of cancer: the time demands of cancer-related activities and their impact on well-being and quality of life

VERSION DATE: 02/27/2024

reduced transportation access who need to rely on public transit and other means of travel.[9, 10]

2.2 Preliminary Data: The concept of time toxicity in cancer care expands the concept of treatment burden in chronic disease management. Theories such as the Burden of Treatment Theory [11] and Cumulative Complexity Model [12] have highlighted the complexity of treatment burden. Instruments such as the Treatment Burden Questionnaire (TBQ) [13] and the Patient Experience with Treatment and Self-management survey (PETS) [14] collect recall-based data on various aspects of treatment burden including patient workload and its impact on patient well-being. Our proposal will add to the field by creating measures that capture time spent on specific cancer-related tasks (e.g. time in clinics, traveling time), and by exploring how sources of treatment burden interact with specific individual (clinical, demographic, life stage) situations that may or may not make the same cancer-related task burdensome.

In work by our group, we have estimated cancer-related time uses among patients with metastatic breast cancer during initial treatment [15] and among patients with cancer receiving chemotherapy [16]. We have also examined self-reported cancer-related workload among patients with breast cancer and found those with stage III and IV cancer reported disproportionate cancer-related time and workload burdens and found these burdens were associated with worse psychosocial outcomes and lower QOL (*in preparation*). In a study of adolescents and young adults with cancer, we found that those with the most intensive cancer treatments more often believed that cancer would negatively impact their plans for work and/or school.[17] In that study, we also found that only a fraction of patients' time is spent interacting with healthcare providers, with substantial time spent traveling to and waiting for care services. The work proposed here will help identify areas to improve time efficiency of care.[15, 16] One of our conclusions was that total time spent on care should not only be reduced, but also distributed more efficiently to allow for more health-care free days.[18] For example, splitting 10 hours of cancer care over two instead of five days gives patients three days that are uninterrupted by care.

We will build on our prior work and comprehensively measure cancer-related time burdens. For this, we will use a customized version of the Daynamica mobile application, created by Co-PI [name] and Co-I [name], which is an established, easy-to-use sensor-based tool to collect data automatically on daily activities and time use requiring minimal user input. More details on the app are provided below. Between 2016 and 2020, the Daynamica app has been deployed in multiple research studies [19-23], collecting information from over 2,000 individuals with >20,000 days of time use and well-being data.

SOCIAL PROTOCOL (HRP-580)

PROTOCOL TITLE: Time toxicity of cancer: the time demands of cancer-related activities and their impact on well-being and quality of life

VERSION DATE: 02/27/2024

2.3 Existing Literature: The relevant literature is cited in sections 2.1 and 2.2 above. There is an urgent need for a tool that generates accurate, comprehensive, and timely measures of logistic toxicity.

3.0 Study Endpoints/Events/Outcomes

3.1 Primary Endpoint/Event/Outcome:

Aim 1: Summary measures of time use by activity and trip type; for each activity/trip type, the number of minutes per day spent on that activity, the number of separate episodes, and the number of days per week on which that activity occurs

Aim 2: Daily well-being, as measured by the American Time Use Survey

Aim 3: Time toxicity score

3.2 Secondary Endpoint(s)/Event(s)/Outcome(s): overall quality of life, emotional health, symptoms, financial toxicity

4.0 Study Intervention(s)/Interaction(s)

4.0 Description: A total of 80 individuals receiving treatment for metastatic breast or advanced stage ovarian cancer will be asked to 1) complete a baseline survey and install the Dynamica mobile app on their smartphone; 2) carry the smartphone for 28 consecutive days while outside the home; 3) keep smartphone location and motion services active; 4) confirm and correct (if needed) smartphone-detected activities and trips; 5) use the app interface to provide additional information on activities and trips related to cancer treatment tasks; 6) complete daily surveys regarding well-being; and 7) at the end of the 28 day period, complete an online survey. Individuals who do not install and use the Dynamica mobile app after completing the consent process and baseline survey will be replaced and not count toward the goal sample size of 80 participants.

5.0 Procedures Involved

5.1 Study Design: Observational cohort study

5.2 Study Procedures: All participant interactions fall under Aim 1. Aims 2 and 3 involve analysis of data collected under Aim 1.

A total of up to 100 individuals currently undergoing treatment for metastatic breast or advanced stage ovarian cancer (frontline, maintenance or for recurrence) will be invited to participate in the study. Participation in the study will not affect clinical treatment decisions. Enrolled participants will be asked to:

- 1) Complete a baseline survey (paper or online per personal preference).
- 2) Install the Dynamica app from the Google Play or Apple App Store on their smartphone (we will provide a smartphone with the app pre-installed to participants who do not own one).

SOCIAL PROTOCOL (HRP-580)

PROTOCOL TITLE: Time toxicity of cancer: the time demands of cancer-related activities and their impact on well-being and quality of life

VERSION DATE: 02/27/2024

- 3) Carry the smartphone for 28 consecutive days while outside the home.
- 4) Keep smartphone location and motion services active.
- 5) Confirm and correct (if needed) smartphone-detected activities and trips.
- 6) Use the Dynamica app interface to provide additional information on activities and trips related to cancer treatment tasks and complete daily well-being surveys
- 7) Complete a follow-up survey at 28 days (paper or online per personal preference).

Data collection will include a combination of daily activity data (objective and self-report) and well-being data (self-report) obtained through the mobile app for 28 days, along with baseline and follow-up surveys following completion of the daily data collection (**Table 1**). Details on each measure are provided below.

Table 1. Patient-Report Data Collection Timing and Measures				
Timing	Day 0	--- Daily Mobile App---	Day 28	
Data Tool	Survey	Sensor data	Survey	Survey
Time Use Measures				
Daily time and cancer-related activity type		X	X	
Opportunity time costs	X		X	X
Typical (non-cancer) time demands	X			X
Outcome and Covariate Measures				
Daily well-being, burden			X	
Quality of Life	X			X
Demographics	X			X

Mobile application data. Once installed on a participant's phone, the Dynamica app will capture location information and automatically infers time, type, and location of activities and trips, providing a "calendar view" of each day (see **Figure 1**).

Participants can edit and provide additional details about each activity or trip, allowing them to break them into smaller episodes (e.g., time traveling to/from, waiting for, and receiving treatment) and provide self-reported information on subjective well-being. The datasets produced by the app are summarized at the episode level, with detailed data including type, start time, end time, location (or route for trips), and any additional information solicited from participants.

SOCIAL PROTOCOL (HRP-580)

PROTOCOL TITLE: Time toxicity of cancer: the time demands of cancer-related activities and their impact on well-being and quality of life

[figure not shown]
VERSION DATE: 02/27/2024

Aim 1

Measure and describe objective time use associated with cancer-related healthcare interactions via a mobile health application

[figure not shown]
Daily time use

Daily well-being questionnaire

Aim 2

Characterize associations between measures of cancer-related time use and self-reported well-being, and explore the role of context in modifying these associations

Aim 3

Create a time toxicity summary score based on measures of cancer-related time use and assess its association with psychosocial outcomes.

[figure not shown]

Figure 1. Smartphone app measurements and aims.

For this study, participants will install an app on their personal smartphones for a 28-day period. The app, currently designed to capture common activities, e.g. home, work, shopping, education, eating out, leisure/recreation, car, bike, bus, will be modified to allow users to indicate and annotate cancer care-related activities. When a cancer care-related activity is reported, participants will be prompted to provide additional information on three items: wait time, time with the provider, and time spent receiving treatment or imaging. If participants repeatedly visit the same care location, these episodes will be automatically recognized such that participants need only provide the additional information. At the end of each day, participants will be asked to complete a short (<5 minute) 8-item survey, including questions regarding any phone calls or other activities that day related to cancer that were not otherwise reported, and time spent on those activities. The survey will also include questions on well-being based on the American Time Use Survey: two positive emotion questions (happy and meaningful) and four negative emotion questions (sad, painful, stressful, and tired). These questions will generate episode-level well-being measures, and will be used to generate outcome variables of daily emotional well-being: (1) U-Index at the person-day level: the proportion of time an individual spends in an unpleasant state during the 24-hour period, with an unpleasant state defined as the individual having a negative emotion more intense than any positive emotions; (2) Duration-weighted sum of average happiness,

SOCIAL PROTOCOL (HRP-580)

PROTOCOL TITLE: Time toxicity of cancer: the time demands of cancer-related activities and their impact on well-being and quality of life

VERSION DATE: 02/27/2024

meaningfulness, sadness, pain, stress, and tiredness scores during a 24-hour period at the person-day level.

Survey data. Additional patient-reported outcomes will be collected at baseline and 28 days (following completion of mobile app data). Measures will be collected on paper or via online surveys in REDCap per participant preference. Study outcomes include reliable and validated measures used previously by the study team and will be scored following standard procedures.

Demographics: Demographic characteristics collected will include age, sex, race/ethnicity, household income, education, insurance status, relationship status, parenting and caregiver status, employment status, and zip code to assess rurality and distance from clinic.

General Quality of Life: QOL is a multi-dimensional concept including domains of physical, psychological, social health, and overall life satisfaction.[27] We will measure QOL using the Functional Assessment of Cancer Therapy - General (FACT-G) questionnaire (39 items).[31]

Depression and Anxiety: Symptoms of anxiety and depression will be measured using the Hospital Anxiety-Depression Scale (HADS). This measure consists of 14 items rated on a 4-point scale and provides separate scores for anxiety and depression, including cut-offs for potentially clinically relevant anxiety and depression.

Distress: We will measure cancer-related distress using the National Comprehensive Cancer Network Distress Thermometer, a single-item tool measuring distress on a scale from 0-10 with an accompanying problem list of potential contributing issues, including practical, physical, family, emotional, and spiritual concerns.[33, 34]

Symptom Management: Breast and ovarian cancers and their treatments can result in significant side effects and symptom burden for patients and these symptoms can increase healthcare utilization while decreasing QOL. The MD Anderson Symptom Inventory (MDASI) is a multi-symptom patient-reported measure of 13 core symptoms that are common and often severe, with impacts on functioning, in patients with cancer.[35]

Opportunity Costs: The Oncology Opportunity Cost Assessment Tool (OOCAT) evaluates opportunity costs - including time spent seeking care, lost wages, lost leisure time, and other indirect costs associated with seeking cancer care.[36] The 18-item instrument includes six domains: travel, appointments, work and school, home, health system, and caregiver burden.

Work, Insurance and Financials: We will measure financial toxicity using the Comprehensive Score for Financial Toxicity (COST) instrument, an 11-item questionnaire validated in individuals with cancer.[37] We will also measure current employment status, days missed due to illness, and health insurance coverage using

SOCIAL PROTOCOL (HRP-580)

PROTOCOL TITLE: Time toxicity of cancer: the time demands of cancer-related activities and their impact on well-being and quality of life

VERSION DATE: 02/27/2024

validated measures derived from the American Cancer Society Study of Cancer Survivors II [38] and National Health Interview [39] surveys.

Patient-reported time burden: We will ask respondents to add free-text comments, for example to describe circumstances in their life that may have amplified or reduced the cancer-related time burdens.

Medical record data. Participant medical data, including diagnosis, treatments received and dosage, adverse events, comorbidities and healthcare encounters, will be abstracted from the medical records at each site and entered into REDCap.

5.3 Follow-Up: Survey data will be collected before the study and immediately after participants finish using the app for 28 days.

Individually Identifiable Health Information: We will obtain written HIPAA agreement from participants. Dynamica uses GPS location data to infer activity type and trip mode; such detailed location data constitute Protected Health Information (PHI).

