14.0 Risks to Participants

- 14.1 Foreseeable Risks: This study has few risks. We identified the following 2 possible risks to subjects:

Risk to confidentiality: Inadvertent breaches of confidentiality by investigators or their staff are unlikely but may occur. Identifying information will be kept private and all identifiers will be removed prior to any data being given to researchers. The records will be identified only with a unique ID number on an encrypted database. Data transfer will only occur with de-identified data with encrypted transfer of all information containing protected health information between participants and study databases.

The Dynamica app records information about daily activities, including relevant locations such as home and work. These data are potentially highly sensitive, and hence there is a non-trivial risk of loss of confidentiality and privacy if the data are accessed inappropriately. We have put multiple safeguards in place to ensure data security, including strict guidelines about which study team members have access to

SOCIAL PROTOCOL (HRP-580)

PROTOCOL TITLE: Time toxicity of cancer: the time demands of cancer-related activities and their impact on well-being and quality of life

VERSION DATE: 02/27/2024

which data, and how the data are to be used. In addition, the Dynamica app empowers users by providing an interface to review and edit all data collected (e.g., change start/end times, modify activity types and trip modes, etc.). Further, users are always free to turn off the app during time periods where they would prefer not to be tracked.

Discomfort while interacting with the app or answering survey questions: There is a possibility that some participants may feel uncomfortable interacting with the app or when answering survey questions which may remind them of their cancer diagnosis. They will be reminded that they can skip any questions or discontinue at any time.

The data from these studies will not be used to direct patient care. Therefore, participation in this study will have no influence on the care the patient receives nor will it influence treatment decisions.

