17.0 Statistical Considerations

17.1 Data Analysis Plan:

SOCIAL PROTOCOL (HRP-580)

PROTOCOL TITLE: Time toxicity of cancer: the time demands of cancer-related activities and their impact on well-being and quality of life

VERSION DATE: 02/27/2024

Aim 1: For the time use component, we will focus on characterizing the distributions of summary measures of time use by activity and trip type. Similar to our previous work,[19] we will compute, for each activity/trip type, the number of minutes per day spent on that activity, the number of separate episodes, and the number of days per week on which that activity occurs. For common activities and trip types (home, work, driving), means and variances of these measures generally provide useful summaries of how individuals engage in these activities. For less common activities such as cancer care-related activities, total number of episodes, total time spent, and the mean/variance of episode duration may be more meaningful summary measures.

Aim 2: *Qualitative analysis component.* Some individual circumstances (for example, competing time demands, level of support, flexibility of employers) that either buffer against or aggravate the burden cannot be easily ascertained from our app- and survey-based measurements. Therefore, we will examine free-text responses to open-ended survey questions. All entries will be transcribed. We will examine themes and consistencies. Two coders will read the entries and apply the constant comparative method to analyze and code data. As themes are identified, coders will return to the transcripts to reread and recode excerpts, thus ensuring that themes are grounded in data. A computer-assisted qualitative data analysis system (NVivo) will be used to enhance these analyses.

Aim 3: *Generating a time toxicity score.* Using the Dynamica app-based spatiotemporal data collected in Aim 1, we will calculate time-based measures for each individual that characterize the degree of burden and disruption to daily life associated with receiving treatments for cancer. We propose to quantify four subtypes of time toxicity: episodic toxicity, travel toxicity, opportunity toxicity, and scheduling toxicity. Each of these subtypes is described by a different set of time-based measures. **Table 2** lists the four subtypes and describes the time-based measures that we will calculate to characterize each subtype.

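### The abstracted healthcare encounters are never used to check the app's cancer-care data, and no rule separates a day without care from a day on which care was not captured

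*Combined protocol and SAP*

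**What the plan says.** Under section 5.2 the app "automatically infers time, type, and location of activities and trips, providing a 'calendar view' of each day". Participants are asked to "Confirm and correct (if needed) smartphone-detected activities and trips", and the app "will be modified to allow users to indicate and annotate cancer care-related activities". Waiting, provider and treatment times come from the participant: "When a cancer care-related activity is reported, participants will be prompted to provide additional information on three items". Two features catch some visits that would otherwise be missed. For repeat visits to the same care location, "these episodes will be automatically recognized such that participants need only provide the additional information". The end-of-day survey also asks about cancer-related activities not yet reported and the time they took. Section 14.1 adds that "users are always free to turn off the app during time periods where they would prefer not to be tracked".

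The score in section 17.1 (Aim 3) is app-based: "Using the Dynamica app-based spatiotemporal data collected in Aim 1, we will calculate time-based measures for each individual". The Aim 2 models in section 17.3 use the daily time-use measures calculated in Aim 1.

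Section 5.2 (Medical record data) provides that diagnosis, treatments, "adverse events, comorbidities and healthcare encounters, will be abstracted from the medical records at each site and entered into REDCap". Section 18.2 describes the same abstraction at outside sites, including hospitalizations and other cancer-related encounters. No part of section 17 gives these data a role in the time-use measures.

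**The concern.** In a study meant to measure burden, low burden must be distinguishable from low capture. A visit can escape the app if the app is off, the phone is left behind, or a first visit to a location is not annotated. If the rest of that day is observed and the recall item does not pick the visit up, three things follow:

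- the Aim 1 visit and time totals are too low;
- the count and hours measures in Table 2 are too low, and because they are standardised across participants, unequal capture changes how participants rank on the Aim 3 score;
- in Aim 2 the day joins the no-visit comparison days, and the past-week exposure in the aggregated models is understated on later days.

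The planned monitoring would not show this. The dashboard (sections 17.4 and 19.1) summarises what the app recorded, so it cannot reveal a visit that went unrecorded. The record could, but no such comparison is planned.

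**Working it through.** **Inputs** (section 17.2, Aim 2): 80 participants, 28 days, appointment probability p from Beta(2,4), residual SD 1.5, within-person correlation about 0.4, effect 0.25 units, stated power about 90%. Two-sided alpha of 0.05 is assumed, since the Aim 2 text gives none. The capture share s is also assumed, because the documents give no figure.

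**Reproducing the plan's power.** For Beta(2,4), E[p] = 1/3 and E[p²] = 1/7, so E[p(1−p)] = 4/21 = 0.1905. A correlation of 0.4 with residual variance 2.25 implies a between-person variance of 1.5. From within-person information:

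SE = √(2.25 / (80 × 27 × 0.1905)) = 0.074

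Power = Φ(0.25/0.074 − 1.96) = 92.2%. Simulating the random-intercept model gave 91.9% (10,000 runs). Both are close to the stated 90%.

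**Effect of missed visits.** Suppose a share s of visit days is captured at random, the rest are coded as no-visit days, and there are no false positives. The expected within-person slope is

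0.25 × E[p(1−p)] / (E[p] − s·E[p²])

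- s = 0.9: 0.25 × 0.1905 / (0.3333 − 0.1286) = 0.233
- s = 0.8: 0.25 × 0.1905 / (0.3333 − 0.1143) = 0.217
- s = 0.6: 0.25 × 0.1905 / (0.3333 − 0.0857) = 0.192

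The share of comparison days that are really visit days is p(1−s)/(1−ps) at p = 1/3. The simulation (4,000 runs per row) agrees with the formula:

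| Captured | Slope, formula | Slope, simulated | Power, simulated | Visit days among comparison days |
|---|---|---|---|---|
| 100% | 0.250 | 0.251 | 92% | 0% |
| 90% | 0.233 | 0.232 | 88% | 4.8% |
| 80% | 0.217 | 0.219 | 81% | 9.1% |
| 60% | 0.192 | 0.194 | 64% | 16.7% |

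**Whole-day loss is a separate matter.** Section 17.2 (Aim 1) expects about 20 to 28 observations per person. With perfect capture on 20 days each, simulated power is about 80% and the slope stays at 0.25. Losing whole days at random costs precision; coding missed visits as no-visit days also biases the estimate.

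**The case against.** The strongest reply is that the app offers several routes to a visit: passive sensing, recognition of repeat care locations, annotation, and the end-of-day question. A day is misclassified in the same-day Aim 2 model only if all of these fail and the daily survey is still completed. On a day of complete disengagement there is no well-being outcome, so the day normally drops out. Aim 1 is also defined as measurement by a mobile application, and the record may miss care given elsewhere and may not hold durations.

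This narrows the mechanism considerably but does not remove it. Recognised visits still need the participant to supply the waiting, provider and treatment times. The recall item relies on the same participant on the same day. The past-week models and Aims 1 and 3 do not require a completed survey on the day of the missed visit.

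A reader might infer three stronger things, none of which the documents support:

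- **Care counts only if the participant logs it.** Automatic inference and repeat-location recognition contradict this.
- **The plan scores missed care as zero.** No coding rule is stated. Section 17.1 says the score can be computed from imputed or complete-case data, although as a general property and not as a rule for this study.
- **Sicker patients log less, so the Aim 3 association reverses.** The documents give no data on logging by health status, and no calculation here shows a reversal. The Aim 3 model also adjusts for the baseline survey measure.

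**Conclusion.** The gap is real and worth closing: a second source on care encounters is collected, yet nothing in section 17 uses it to check or complete the app data, and absence of care is not distinguished from absence of capture. Under random misses coded as no-visit days, the loss in Aim 2 is small at 90% capture (0.25 becomes about 0.23, power 88%) and material at 60% (about 0.19, power 64%). These figures depend on an assumed capture share, and if misses cluster on bad days the bias could differ in size and direction. No size can be given for Aims 1 and 3 without a capture rate, which the proposed linkage would supply.

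**What to change.** In sections 17.1 and 17.3:

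1. Define an observed app day. Treat app-off or unobserved days as missing, not as zero care.
2. Match abstracted encounter and treatment dates to app days by study ID. Report the share of record-documented in-person encounters that the app captured, overall and by participant.
3. Define an either-source care-day flag: an app-recorded visit or a record-documented in-person encounter. Keep app-only visits, because the site record may miss outside care. With this flag, rerun the Aim 2 appointment-day contrast and the Aim 1 and Aim 3 visit-day and appointment-count measures, beside the app-only analysis.
4. Do not fill in mean durations in the main analysis, since this would flatten the duration-variation measure in Table 2 and pull poorly captured participants towards average. Any duration imputation should be a flagged sensitivity analysis.

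The cost is some text and a modest linkage, with no added burden on participants. The linkage requires encounter dates to be abstracted at day level, which the documents do not confirm and the abstraction form should specify. The record will correct visit days and counts more readily than hours.
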